6.1 Anticipated benefits

A more equitable breast cancer screening program, through higher attendance rates among immigrants and increased knowledge about the health care system in Norway among immigrants.

6.2 Anticipated risks

The risk with this study is that the direction of the effect estimate is opposite of our hypothesis – i.e., that fewer immigrant women attend the screening program. Attendance in the screening program must be based on a voluntary choice. This study is designed to increase equity in the program and provide immigrants with equal opportunities for access to health care. If our intervention further increases the gap between the general and the immigrant population, we will consider it an adverse event, which will lead to termination of the study. There can be many reasons for such an event, for instance confusion due to

neighbours, friends or family being randomised to receive invitations in another language than the participant. Furthermore, just because the participant is born in a country, does not mean they speak the language of that country. On the other hand, participants receiving invitations in their own language may feel a pressure to attend, which goes against the principle that attendance should be based on voluntary choice.

6.3 Data and Safety Monitoring Board

To avoid the adverse event described above, we will recruit an independent Data and Safety Monitoring Board (DSMB). A DSMB is an independent review board consisting of experienced researchers/trialists that monitor the data in the trial in order to ensure safety. The DSMB will review the data at 3 set time points: At the end of Q1, Q2, and Q3 in 2021. A dedicated research assistant managing the data at the Cancer Registry of Norway in accordance with the data management plan will send aggregate data to be reviewed by the board. If the data match the termination criteria defined in chapter 7, data collection in the study will stop. The sending of aggregate data circumvents the necessity of an ethical review board approval.

Safety and Monitoring Board		
Name	Position	Institution
[name]	Researcher	Cancer Registry of Norway
[name]	Breast radiologist	Vestre Viken Health Trust
[name]	Leader, dept. of registry informatics	Cancer Registry of Norway

7 Statistical considerations

7.1 Statistical design

This study will be designed a superiority trial with the difference in attendance rate between the study and control arm as primary outcome. Bivariate tests will be used to analyze the primary outcome. In addition, effect estimate plots for the total effect and each specified subgroup will be made using rate ratios, corresponding 95% confidence intervals and p-values.

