7.7 Specification of subgroups.....	11
7.8 Treatment of missing, unused, spurious data	11
8 Data management.....	11
9 Amendments to the research protocol.....	12
10 Deviations from the research protocol	12
11 Statements of compliance.....	12
12 Informed consent process.....	12
13 Suspension or premature termination of the clinical study.....	12
14 Publication policy	13
15 Bibliography.....	13
Appendix – invitation letter and leaflet.....	15

1 Introduction

This two-armed, parallel group, blinded, pragmatic randomised controlled trial is designed to examine the potential superior effect on attendance when inviting immigrant women targeted BreastScreen Norway to mammographic screening in their presumed language of origin and in Norwegian versus in Norwegian only. The study is aimed at enrolling 14,000 immigrant women.

Breast cancer is the most common cancer among women in Norway and word-wide (1). In Norway, almost 3700 women were diagnosed with breast cancer and 600 died from the disease in 2017 (2). The national screening program for breast cancer, BreastScreen Norway, started in 1996 (3). The primary goal of the screening program is to reduce breast cancer mortality through early detection. The annual attendance rate in the program is about 75%, however immigrant women have a substantially lower attendance rate compared to non-immigrant women (4). A qualitative study have highlighted some of the barriers for immigrants to attend screening, among those were the invitation letter and language (5).

BreastScreen Norway and the Norwegian colorectal cancer screening program joined forces and applied for funding to investigate whether invitations to screening in a major language in invited immigrant's country of birth would increase attendance. The application successfully asked for funding for three studies: a randomized controlled trial (RCT) of inviting women to BreastScreen Norway in their language of origin, a similar RCT for the colorectal cancer screening program, and a qualitative study.

This protocol covers the first of the three studies proposed, in which we will perform an RCT to investigate whether receiving a translated version of the invitation letter and information leaflet ("invitation letter") in the official language of the country of birth ("official language") increases the attendance rate of immigrant women invited to BreastScreen Norway.

2 Study Description

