3.4 Risks and anticipated adverse events that are to be assessed

The risk of this study is that an invitation in the major official native language of the women's country of birth will lead to lower attendance.

4 Project methodology

We will run a randomized clinical trial (RCT) in five language groups, sending an invitation letter in a major official language in addition to Norwegian to a randomly assigned half of the women, while the other half will receive an invitation only in Norwegian according to normal procedures (randomization 1:1 within each language group). Attendance rates, attendance among the invited, in the two arms will be compared. Based on results of 2018 the study by Bhargava et al. we will include women born in Poland, the Philippines, Pakistan, Somalia, and Arabic speaking countries (Iraq, Syria, Lebanon and Palestine) (4). These women have a low attendance rate in BreastScreen Norway and the number of women in the target group is sufficient to detect a difference in attendance (see chapter 7.4 for minimal effect size detectable). Descendants of immigrants will not be included in the RCT. All information material, including the invitation letter, information leaflet, response letter, and invitation reminder, will be translated by a professional agency, quality assured by professionals and tested by health professionals and women in the target group. The translation work started in January 2020, while a pilot of the trial will be performed during the fall 2020. The RCT will start January 2021 and run for one year. Quality assurance will run throughout 2021. Results will be analysed, interpreted, and disseminated during 2023.

5 Study design

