5.1 General

5.1.1 Description

We will perform a *randomized controlled trial*. The study has *two arms* to which women can be randomized – an intervention arm and a control arm. The intervention arm consists of five different *strata*: the Arabic stratum, the Filipino stratum, the Pakistani stratum, the Polish stratum, and the Somali stratum. As the randomization in this study is stratified, women are first divided into strata, and then randomly assigned to either the intervention or the control arm. The study has a *parallel group design*, meaning there are no crossovers between the two arms. The intervention arm will only get the intervention, and the control arm will never receive the intervention. As the study is *blinded*, women are de-identified before they are randomized and will remain pseudonymized to the researchers throughout the study period. The study is *pragmatic*, meaning it will be embedded within BreastScreen Norway, and data collection will take place in an everyday screening setting. In summary, this is a two-armed, parallel group, blinded and pragmatic randomized controlled trial.

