5.1.2 Primary endpoint

The primary endpoint of this study is **attendance**, defined as the number of women attending a screening examination among the number of women invited to a screening examination during the study period. The study will compare attendance in the two groups.

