7.2 Trial participants and expected attendance

In total, we expect about 7400 women to be invited to the RCT, including 2200 women from Poland, 1400 from the Philippines, 1500 from Pakistan, 1300 from Arabic countries, and 500 from Somalia (Table X). Women within our five strata will be identified in the databases of BreastScreen Norway. These five strata represent the most common immigrant groups in the program. The different strata have different attendance rates, and we expect attendance rates in the control arms in the trial to be similar to those observed in 1996-2014.

Table 1. Target group 1996-2015 adapted from Bhargava et al 2018 (4), and estimated numbers for invited (total and each arm) and attended (control arm) in 2021

Country (language)	Target group 1996-2014 (n)	Expected to be invited in 2021 (n)	Attendance rate 1996-2014 (%)	Expected to attend in the control group 2021 (n)
Arabic	2600	1300 (650 in each arm)	40%	260
English	2700	1400 (700 in each arm)	54%	378
Polish	4300	2200 (1100 in each arm)	50%	550
Somali	1000	500 (250 in each arm)	14%	35
Urdu	3000	1500 (750 in each arm)	34%	255
Total	13 600	7400 (3700 in each arm)	40%	1480

Power calculations are performed for two independent sample proportions with a statistical power ($1-\beta$, where beta is the type II error rate) of 0.8 and significance level (α , type I error rate) of 0.05. To show that differences $\geq 10\%$ is statistically significant for attendance rates in the control group given in Table X, at least 356 invitations need to be sent to women from Poland, 379 to women from the Philippines, 373 to women from Pakistan, 388 to women receiving invitation in Arabic and 241 to women from Somalia (Table 2). Estimated number of invitations and sample size needed in the study arm to show that a 10% increase in the study arm compared to the control arm is statistically significant.

Table 2: Estimated number of invitations in the study arm and sample size needed in the study arm to reach statistically significant increase of 10% in attendance in the study arm (statistical power ($1-\beta$, where beta is the type II error rate) of 0.8 and significance level (α , type I error rate) of 0.05)

Stratum	Estimated number of invitations in the study arm (n)	Sample size needed in the study arm (n)
Arabic	650	388
English	700	379
Polish	1100	356
Somali*	250	241
Urdu	750	373
Total	3700	388

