7.8 Treatment of missing, unused, spurious data

We do not expect any data to be truly missing.

8 Data management

After trial participants are identified, a pseudonymized dataset will be extracted, and randomization will be performed. The randomization variable will be coded into the screening database, and the individual trial participant will be automatically invited in the correct language. Data on invitation and attendance will be automatically registered in the screening databases, as per current routines.

The invitation system registers when an invitation is sent, at which point an invitation number (accession number) is created. When the woman shows up for screening, a radiographer registers the woman in the dedicated screening software. Errors in this dataflow are extremely rare, but a quality assurance script will be run once every month to make sure all women with a screening result have data on attendance. There will be no external data review. Tables and other statistics from this quality assurance will be presented to the project leader and principal investigator once every month.

All data system security is handled as per the routines of the Cancer Registry of Norway. Data is stored in an encrypted and secured database for sensitive information, with external backups. A data security team at the Cancer Registry of Norway ensures that all security procedures are followed and that security systems are up to date. Please see the **data management plan** for a more thorough description of the data management in this project.

The data used only for this study is the randomization variable. This information will be retained until 31st of December 2030.

9 Amendments to the research protocol

The Research Protocol may require to be amended during the conduct of a clinical study. Any amendment to the Research Protocol will be agreed upon between the project leader and the principal investigator. The amendments will be approved by the Norwegian Directorate of Health which accepted this study (20/33385-2).

10 Deviations from the research protocol

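### The primary comparison ignores the five language groups used for randomisation; a test stratified by group would be slightly more precise at almost no cost.

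*Protocol*

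**What the plan says.** Protocol section 7.1 makes the difference in attendance rate between arms the primary outcome and gives the method in one sentence: "Bivariate tests will be used to analyze the primary outcome". No specific test is named. The same section adds that "effect estimate plots for the total effect and each specified subgroup will be made using rate ratios", without saying that the total takes account of language group.

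The design is stratified. Section 4 specifies "randomization 1:1 within each language group", and section 5.1.1 says "As the randomization in this study is stratified, women are first divided into strata". Section 7.2 acknowledges that "The different strata have different attendance rates"; Table 1 expects 40% (Arabic), 54% (English), 50% (Polish), 14% (Somali) and 34% (Urdu) in the control arms. Language group otherwise appears only as separate group-level analyses (sections 3.1.2 and 7.7).

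Two further statements bear on balance between arms. Section 8 places randomisation before invitation: "After trial participants are identified, a pseudonymized dataset will be extracted, and randomization will be performed". Section 5.1.2 defines attendance as "the number of women attending a screening examination among the number of women invited to a screening examination during the study period", so the denominator is the women invited.

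**The concern.** The trial stratifies on a strong predictor of attendance, and the stated overall test then leaves that predictor out. The variation between groups stays in the standard error of the crude comparison although a stratified analysis would remove it.

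How this shows depends on balance among the women analysed:

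- If each group is split exactly 1:1, the crude and Mantel-Haenszel risk differences coincide. The crude standard error is then too wide and the test slightly conservative.
- If balance is only approximate, the crude test moves towards its nominal level, but the estimate carries real noise from chance differences in language mix between the arms.

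Exact balance is not assured, because women are randomised first and counted only if invited during the study period.

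At stake is a little power and a slightly wider interval for the overall result. The group-level analyses of section 7.7 are unaffected.

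**Working it through.** **Inputs.** Table 1, women per arm and control rate: Arabic 650, 0.40; English 700, 0.54; Polish 1,100, 0.50; Somali 250, 0.14; Urdu 750, 0.34. The groups sum to 3,450 per arm; the printed total is 3,700. Section 1 gives a third size ("The study is aimed at enrolling 14,000 immigrant women"), that is 7,000 per arm. All three are carried through with the same group mix. Alpha is 0.05 (section 7.2), and the overall difference is 3 points (Table 3).

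**1. The plan's own figure.** Table 2 gives 388 for the total, 40% against 50%. The two-sided two-proportion formula gives

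n = [1.96·√(2·0.45·0.55) + 0.8416·√(0.40·0.60 + 0.50·0.50)]² / 0.10² = 387.3, rounded up to 388.

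It reproduces, so two-sided testing is used below. The same formula gives 74.5% power for 40% against 43% at 3,700 per arm, so the overall comparison is already below 80% at 3 points.

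**2. Variance split.**

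- Pooled rate: 1,478/3,450 = 0.4284. Pooled variance: 0.4284·0.5716 = 0.2449.
- Within groups: (650·0.2400 + 700·0.2484 + 1,100·0.2500 + 250·0.1204 + 750·0.2244)/3,450 = 803.28/3,450 = 0.2328.
- Between groups: 0.2449 − 0.2328 = 0.0120 (unrounded inputs).
- Variance ratio 1.0517; standard error ratio √1.0517 = 1.0255.
- Somali share of the between-group part: 250·(0.14 − 0.4284)²/3,450 = 0.0060, or 50%.

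**3. Type I error of the crude test.** Let f be the fraction of between-group variance that remains in the estimate. Then alpha = 2·[1 − Φ(1.96·√(0.2449/(0.2328 + f·0.0120)))].

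- f = 0, exact balance: 4.4%.
- f = 0.5, half of a balanced randomised pool invited (an assumption): 4.7%.
- f = 1, independent 1:1 allocation: 5.0%.

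The stratified test is at 5.0% in all three.

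**4. Power at a common +3 points.** Power = Φ((0.03 − 1.96·SE₀)/SE_true). The crude SE₀ is √(2·0.4434·0.5566/n), where 0.4434 is the average of the two arms' pooled rates. The stratified SE₀ uses the within-group variances. SE_true uses the pooled variances for the crude test under independent allocation, and the within-group variances otherwise. At 3,450 per arm:

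- Crude, independent allocation: Φ((0.03 − 0.02344)/0.01196) = 70.8%.
- Crude, exact balance: Φ((0.03 − 0.02344)/0.01166) = 71.3%.
- Stratified: Φ((0.03 − 0.02287)/0.01166) = 73.0%.

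| Per arm | Crude power | Stratified power | 95% CI half-width, crude / stratified (points) |
|---|---|---|---|
| 3,450 | 70.8-71.3% | 73.0% | 2.344 / 2.287 |
| 3,700 | 73.8-74.3% | 75.9% | 2.264 / 2.208 |
| 7,000 | 94.7-95.1% | 95.6% | 1.646 / 1.605 |

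Simulation agrees (400,000 trials per setting, 3,450 per arm). Power, crude against Cochran-Mantel-Haenszel, was 71.5% against 73.0% with exact balance and 70.8% against 72.9% with independent allocation. Under no effect the rejection rates were 4.5% against 5.1% and 5.0% against 5.0%.

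**5. Equivalent sample size.** To match the stratified interval width, a crude analysis needs 5.17% more women: 357 on 6,900, 383 on 7,400 or 724 on 14,000.

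**6. Sensitivity, 3,450 per arm.**

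- Unequal effects averaging 3 points: stratified power is 73.1% (common rate ratio), 72.5% (only Arabic, Somali and Urdu respond) or 73.5% (only English and Polish respond), against 70.8-71.4% crude.
- Somali control rate 30% instead of 14%: variance ratio 1.030, power 70.6-70.9% against 71.9%, a gain of 1.0-1.2 points.

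**The case against.** The strongest case for leaving the text alone has three parts.

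*It belongs in the SAP, and nothing is wrong.* No test is named, an SAP not at hand may stratify, and a crude test is valid with a type I error never above nominal. The power calculation also treats two independent proportions, so planning and analysis agree. Validity is conceded. But calling the test bivariate is a stated choice and not a gap, and an SAP with a stratified primary test would have to depart from it.

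*The loss is overstated for the balanced design in Table 1.* With equal arms in every group the two estimates are identical and only the crude standard error is conservative. That is correct. It puts the power loss at 1.6-1.7 points at the Table 1 sizes, against 2.1-2.2 under independent allocation. Half of the between-group variance also rests on one small group and its 1996-2014 attendance rate.

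*A late switch may cost more than it returns.* On the protocol's timetable data collection is over, group-level attendance reviews were planned at Q1, Q2 and Q3 (sections 6.3 and 7.5), and the interval narrows by only about 0.06 points at 3,450 per arm. This is the most serious point. It is why the change needs a dated declaration and why the crude analysis should stay alongside. It does not remove the case for analysing by the groups already used for randomisation.

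**Conclusion.** The concern holds as a minor, optional improvement. The stated overall test leaves out the randomisation strata and gives away about 2 points of power (1.6 to 2.2) for a 3-point difference at 3,450 or 3,700 per arm, and under 1 point at 7,000. Bias and validity are not in question, and only a borderline overall result could change. Stratifying does not cure the separate shortfall below 80% power at 3 points for the Table 1 sizes.

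The size rests on the Table 1 rates and group mix, on two-sided testing at 0.05, and on reading bivariate as unadjusted. It does not need a common effect across groups, but it roughly halves if Somali attendance is nearer 30%.

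**What to change.** In section 7.1, make the primary overall analysis a Cochran-Mantel-Haenszel test stratified by the five language groups, with the Mantel-Haenszel risk difference and its 95% CI. Keep the crude bivariate comparison as a sensitivity analysis.

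Date the change, declare it as an amendment, and state whether results by arm had been seen when it was made, and by whom. That statement should cover the planned quarterly reviews and the monthly quality-assurance tables that section 8 sends to the project leader and principal investigator (not said to be by arm).

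The cost is one sentence plus the declaration. No new data are needed: the strata were formed before randomisation and follow from country of birth, which section 7.4 already lists for extraction. The real cost is the explanation that a change made after the planned data collection requires.

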7.2 Trial participants and expected attendance

In total, we expect about 7400 women to be invited to the RCT, including 2200 women from Poland, 1400 from the Philippines, 1500 from Pakistan, 1300 from Arabic countries, and 500 from Somalia (Table X). Women within our five strata will be identified in the databases of BreastScreen Norway. These five strata represent the most common immigrant groups in the program. The different strata have different attendance rates, and we expect attendance rates in the control arms in the trial to be similar to those observed in 1996-2014.

Table 1. Target group 1996-2015 adapted from Bhargava et al 2018 (4), and estimated numbers for invited (total and each arm) and attended (control arm) in 2021

Country (language)	Target group 1996-2014 (n)	Expected to be invited in 2021 (n)	Attendance rate 1996-2014 (%)	Expected to attend in the control group 2021 (n)
Arabic	2600	1300 (650 in each arm)	40%	260
English	2700	1400 (700 in each arm)	54%	378
Polish	4300	2200 (1100 in each arm)	50%	550
Somali	1000	500 (250 in each arm)	14%	35
Urdu	3000	1500 (750 in each arm)	34%	255
Total	13 600	7400 (3700 in each arm)	40%	1480

Power calculations are performed for two independent sample proportions with a statistical power ($1-\beta$, where beta is the type II error rate) of 0.8 and significance level (α , type I error rate) of 0.05. To show that differences $\geq 10\%$ is statistically significant for attendance rates in the control group given in Table X, at least 356 invitations need to be sent to women from Poland, 379 to women from the Philippines, 373 to women from Pakistan, 388 to women receiving invitation in Arabic and 241 to women from Somalia (Table 2). Estimated number of invitations and sample size needed in the study arm to show that a 10% increase in the study arm compared to the control arm is statistically significant.

Table 2: Estimated number of invitations in the study arm and sample size needed in the study arm to reach statistically significant increase of 10% in attendance in the study arm (statistical power ($1-\beta$, where beta is the type II error rate) of 0.8 and significance level (α , type I error rate) of 0.05)

Stratum	Estimated number of invitations in the study arm (n)	Sample size needed in the study arm (n)
Arabic	650	388
English	700	379
Polish	1100	356
Somali*	250	241
Urdu	750	373
Total	3700	388

Since the attendance rates and the possible number to invite differs for each stratum, we also calculated the minimal detectable differences based on expected attendance rates and invitations in the control groups (Table 3). Smaller differences for each stratum will not be considered statistically significant.

Table 3: Expected number of invitations, attendance rate, minimal detectable difference to show statistically significant difference, and estimated lowest attendance rate in the study arm that will be significantly higher than the expected rate in the control arm

Stratum	Expected number of invitations in each arm (n)	Expected attendance rate in control group	Minimal detectable difference	Lowest attendance rate in the study arm that will be significantly higher*
Arabic	650	40%	8%	48%
English	700	54%	8%	62%
Polish	1100	50%	6%	56%
Somali*	250	14%	10%	24%
Urdu	750	34%	7%	41%
Total	3700	40%	3%	43%

*Attendance rate in control group + minimal detectable difference.

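### The protocol gives three trial sizes (14,000; 7,400; 6,900 from the strata) without reconciling them, and the pooled size and rates in the Total rows of Tables 1–3 contradict the strata

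*Protocol*

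**What the plan says.** The Introduction gives one size: "The study is aimed at enrolling 14,000 immigrant women". Section 7.2 gives another: "In total, we expect about 7400 women to be invited to the RCT", and that sentence continues with its components, "including 2200 women from Poland, 1400 from the Philippines, 1500 from Pakistan, 1300 from Arabic countries, and 500 from Somalia". Table 1 repeats the same five stratum counts, for example "1300 (650 in each arm") for Arabic, and closes with a Total of "7400 (3700 in each arm"), an overall control rate of 40% and 1,480 expected control attendees. The figure 3,700 recurs in the Total rows of Tables 2 and 3.

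Table 3 has a column for the "estimated lowest attendance rate in the study arm that will be significantly higher than the expected rate in the control arm". Its footnote defines this as the control rate plus the minimal detectable difference. The Total row prints 3,700 per arm, 40%, 3% and 43%.

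For the stratum requirements, section 7.2 uses a 10-point increase, power 0.8 and significance level 0.05, and says that "at least 356 invitations need to be sent to women from Poland". Section 4 fixes the period: "The RCT will start January 2021 and run for one year".

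**The concern.** Section 7.1 makes the difference in attendance between the two arms the primary outcome. The Total rows of Tables 1–3 are therefore the only place where the protocol states the size, expected control rate and detectable difference for that comparison. If the total does not equal the sum of its parts, and the overall rate depends on that total, a reader cannot say how many women were planned. Nor can the reader judge whether the trial reached its target or what control rate the pooled calculation assumed. The 14,000 adds a third candidate, about twice either of the others.

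**Working it through.** **Inputs (Protocol, Table 1)**

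| Stratum | Target group | Invited | Per arm | Control rate | Control attendees |
|---|---|---|---|---|---|
| Arabic | 2,600 | 1,300 | 650 | 40% | 260 |
| English | 2,700 | 1,400 | 700 | 54% | 378 |
| Polish | 4,300 | 2,200 | 1,100 | 50% | 550 |
| Somali | 1,000 | 500 | 250 | 14% | 35 |
| Urdu | 3,000 | 1,500 | 750 | 34% | 255 |
| **Sum of rows** | **13,600** | **6,900** | **3,450** | **42.8%** | **1,478** |
| Printed Total | 13,600 | 7,400 | 3,700 | 40% | 1,480 |

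**Size.** The target-group column adds up and the attendee column agrees to rounding. The invited column does not: 7,400 − 6,900 = 500, or 500/6,900 = 7.2%. Each stratum's invited count is about half its target group, and half of 13,600 is 6,800. That pattern fits 6,900 better than 7,400.

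**Overall control rate.** 1,480/3,700 = 40.0%, which is the printed figure. From the strata, 1,478/3,450 = 42.84%. Weighting by target group gives (1,040 + 1,458 + 2,150 + 140 + 1,020)/13,600 = 5,808/13,600 = 42.7%. Neither weighting gives 40%.

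**Formula behind Table 2.** The protocol does not state whether the test is one- or two-sided. The two-sided, pooled-variance formula without continuity correction is

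n per arm = [1.960·√(2p̄(1−p̄)) + 0.842·√(p₁(1−p₁) + p₂(1−p₂))]² / (p₂−p₁)², with p̄ = (p₁+p₂)/2.

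For 40% to 50%: [1.960·√0.495 + 0.842·√0.49]² / 0.01 gives 388.

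| Comparison | Formula | Printed |
|---|---|---|
| Arabic, 40% to 50% | 388 | 388 |
| English, 54% to 64% | 379 | 379 |
| Somali, 14% to 24% | 241 | 241 |
| Urdu, 34% to 44% | 373 | 373 |
| Polish, 50% to 60% | 388 | **356** |
| Total, 40% to 50% | 388 | 388 |
| Total, 42.84% to 52.84% | 391 | – |

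Four strata reproduce exactly. Polish must equal the 40% to 50% case, because 50% to 60% has the same p̄(1−p̄) and the same variance sum (0.25 + 0.24). The printed 356 is the value for 30% against 40%. With 1,100 Polish women per arm, power for 50% to 60% is about 99.7%, so this slip changes nothing in practice.

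**Table 3, Total row.** Solving the same formula for the difference at 80% power:

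| Per arm | Control rate | Detectable difference | Power for exactly 3.0 points |
|---|---|---|---|
| 3,700 (printed) | 40% (printed) | 3.21 points | 74.5% |
| 3,450 (strata) | 42.84% (strata) | 3.35 points | 70.8% |

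By the footnote's rule, the study-arm rate is 42.84 + 3.35 = 46.19%, about 46.2%, against the printed 43%. The printed 43% exceeds the stratum-based control rate by 43 − 42.84 = 0.16 points, about 0.2.

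**If 14,000 were the analysed size** (7,000 per arm), the detectable difference would be about 2.3 points and power for 3 points about 95%.

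**The case against.** The strongest reply is that little follows from the error.

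- **The power conclusion hardly moves.** The detectable difference is 3.21 or 3.35 points, and both print as 3% in whole percents. Table 2's Total of 388 depends on the 40%, not on 3,700, and becomes 391 against more than 3,400 available per arm. This stands. What does not survive is the printed size, the 40% and the 43%.
- **The 3% is probably rounded.** With a continuity correction the Table 3 differences are 7.86, 7.53, 6.05, 10.23, 7.13 and 3.24, and these round to all six printed values. Without the correction, English is 7.39, which would round to 7 rather than the printed 8. Rounding therefore cannot be excluded, and the 75% and 71% power figures apply only if 3% is read as exactly 3.0 points.
- **The column heading does not mean 46.2%.** A difference detectable with 80% power is larger than the smallest significant one. At 3,450 per arm and 42.8%, significance starts near 2.3 points, about 45.2%. This is fair as a criticism of the heading. The 46.2% follows the footnote's definition, and 43% fits neither reading.
- **14,000 may be a different quantity.** Screening is every two years, the target group is 13,600, and women are randomised before they are invited, so 14,000 may count women identified rather than invited in one year. This is plausible, but the protocol does not say so and describes the figure as an enrolment aim.
- **Timing.** This version is dated February 2023, after the planned recruitment year, so the correction cannot affect recruitment. It still matters for judging the achieved size against the plan.

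**Conclusion.** The concern holds. The printed total exceeds its own listed components by 500 women (7.2%), and the overall control rate is 2.8 points below what the strata imply. The Total study-arm rate in Table 3 is 43%, where the table's own rule gives about 46.2%. The 14,000 is about twice either other figure and is unexplained. The mismatch itself is certain. That 7,400 is the wrong member of the pair is likely, since text and table agree on every stratum and each is about half its target group, but it is not proved. The effect on pooled power is small: the detectable difference is 3.4 points instead of 3.2. The recomputed power figures assume a two-sided 0.05 test and the formula that reproduces four of the five stratum entries in Table 2. The Polish 356 is a separate slip without practical consequence.

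**What to change.** 1. State one planned size in both the Introduction and section 7.2. Either define what 14,000 counts or remove it.
2. If the strata are right, use 6,900 in total, 3,450 per arm, a control rate of 42.8% and 1,478 expected control attendees in the Total rows wherever these quantities appear. Change the Table 2 Total requirement from 388 to 391. In Table 3, give the Total detectable difference to one decimal (3.4 points) and the study-arm rate as about 46.2%. Alternatively, keep 3 points and state that power is then about 71%.
3. If 7,400 is right, correct the stratum row or rows that are short and recompute the Total rows from them.
4. Change the Polish requirement from 356 to 388 in the text and in Table 2, and leave the Polish control rate at 50%.

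The cost is a restatement of figures. Design, test, allocation and enrolment are unaffected.
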